4.1 Inclusion Criteria

- a) Maintenance hemodialysis therapy 3 times per week for end-stage renal disease
- b) Age 18 – 85 years
- c) ≥ 6 months since hemodialysis initiation
- d) C-reactive protein measured by high sensitivity assay (hsCRP) ≥ 2.0 mg/L at screening and within 10 days prior to randomization (see **Section 4.1.1** for explanation of pre-specified plan for changing the hsCRP threshold while enrollment is underway, if necessary)
- e) Most recent single pool Kt/V ≥ 1.2 within 30 days prior to first screening visit
- f) Negative tuberculosis interferon gamma release assay (e.g. Quantiferon-TB Gold) for tuberculosis unless documented treatment for a) positive PPD, b) positive interferon gamma release assay, or c) tuberculosis.
- g) Negative human immunodeficiency virus (HIV) antibody test, negative hepatitis C Ab test unless viral clearance following direct antiviral therapy is documented, and negative hepatitis B surface antigen positivity.
- h) For women of childbearing potential, willingness to use a highly effective method of birth control for up to 4 weeks after the last dose of anakinra. See **Section 4.2.1** for definition of childbearing potential and acceptable methods of birth control.
- i) Ability to provide informed consent

CONFIDENTIAL

Do not disclose or use except as authorized by the Hemodialysis Novel Therapies Consortium.

4.1.1 Change to CRP Eligibility Threshold

Version 1.0 of the protocol used a CRP threshold of >3 mg/L with the stipulation that the threshold could be decreased to ≥ 2.0 mg/L if needed to facilitate enrollment. In accordance with that stipulation, Version 1.3 of the protocol incorporates the new threshold of ≥ 2.0 mg/L. In addition to enhancing enrollment, using the lower threshold will increase the generalizability of the findings, both in terms of safety and efficacy.

4.2 Exclusion Criteria

- a) Current or anticipated use of a hemodialysis central venous catheter
- b) Acute bacterial infection, including vascular access infection, within 60 days prior to screening unless treated with antibiotics and resolved. Any chronic bacterial infection (e.g., osteomyelitis or bronchiectasis)
- c) Hospitalization within 30 days unless for vascular access procedure
- d) Cirrhosis
- e) Malignancy within the past 5 years with exception of basal or squamous cell carcinoma
- f) Use of an immunosuppressive drug within the past 3 months except low doses of oral corticosteroids (total daily dose ≤ 10 mg/day of prednisone or equivalent)
- g) Receipt of live vaccine within the past 3 months. Live vaccines include Varicella zoster, measles, oral polio, rotavirus, yellow fever, and the nasal spray influenza vaccine
- h) Absolute neutrophil count (ANC) $<2,500$ cells/mm³ (2.5×10^9 cells/L)
- i) Platelet count $<100,000$ /mm³ (100×10^9 /L)
- j) Known allergy to anakinra
- k) Anticipated kidney transplantation, change to peritoneal dialysis, or transfer to another dialysis unit within 9 months
- l) Expected survival less than 9 months
- m) Pregnancy, anticipated pregnancy, or breastfeeding
- n) Incarceration
- o) Receipt of an investigational drug within the past 30 days
- p) Current or anticipated participation in another intervention study

4.2.1 Women of Childbearing Potential

Women of childbearing potential include any female who has experienced menarche and who has not undergone successful surgical sterilization (hysterectomy, bilateral tubal ligation, or bilateral oophorectomy) or is not postmenopausal. Postmenopausal is defined as:

- Amenorrhea for ≥ 12 consecutive months without another cause, or
- Women with irregular menstrual periods and a documented serum follicle stimulating hormone (FSH) level >35 mIU/mL, or
- Women receiving hormone replacement therapy (HRT)

Women who are using oral contraceptives, other hormonal contraceptives (vaginal products, skin patches, or implanted or injectable products), or mechanical products such as an intrauterine device or barrier methods (diaphragm, condoms, spermicides) to prevent pregnancy, or who are practicing

abstinence, or have a partner who is sterile (e.g., vasectomy) should be considered to be of childbearing potential.

Acceptable methods of highly effective birth control include:

- Condom with spermicide
- Diaphragm and spermicide
- Cervical cap and spermicide
- Hormonal contraception

A serum pregnancy test will be done at the local laboratory for women of childbearing potential at the second screening visit, and at weeks 4, 8, 12, 16, 20, 24, and 28.

4.3 Recruitment

Participants at dialysis units affiliated with the practices of a Clinical Center will be screened for eligibility. In addition to active screening of dialysis unit patient rosters by study personnel, informational handouts and brochures may be disseminated at affiliated dialysis units in order to allow potential participants to learn about the study and to contact investigators if interested. All study material must be approved by local IRBs before dissemination to potential study participants.

Dialysis unit laboratory studies, medical records at Clinical Centers, and treatment or history records at local dialysis units will be reviewed to assess eligibility for enrollment. Prior to enrollment, each participant's treating nephrologist will be contacted to assess suitability for enrollment.

Once preliminary eligibility is confirmed, written informed consent will be obtained by a qualified investigator or study site designee during an in-person visit. This visit may take place either at the dialysis unit or at the Clinical Center according to investigator and participant preferences.

Participants may be compensated for study participation. Each Clinical Center is responsible for developing a compensation plan and schedule, and distributing payment.

5 Study Drug

5.1 Description

Anakinra will be supplied in pre-filled syringes as a sterile, clear, colorless-to-white, preservative free solution. Each syringe will contain 100 mg in 0.67 ml solution (pH 6.5) containing disodium EDTA (0.12 mg), sodium chloride (5.48 mg), sodium citrate (1.29 mg), and polysorbate 80 (0.70 mg) in Water for Injection, USP. There will be no modification to the formulation of the manufacturer-supplied anakinra. Saline (0.9%) will be used as the placebo. The study drug will be refrigerated at 2 °C – 8 °C and will be kept away from light.

5.2 Administration of Study Drug

Study drug (100 mg) will be administered via a medication port in the extracorporeal dialysis blood circuit three times per week during the last 30 minutes of the hemodialysis session. The study drug will

be administered by a dialysis unit nurse over 1 minute. There must be at least one calendar day between successive doses, meaning that the drug will not be administered on consecutive days even if dialysis occurs on both days. The duration of treatment is 24 weeks. Participant-specific study drug administration logs documenting each dose administration as well as scheduled doses that are not administered, with the reason for non-administration, will be completed by the dialysis unit nurse administering drug, and provided to the Clinical Center research teams upon resupply visits. Receiving, Storing, Dispensing and Returning Study Drug

5.2.1 Receiving Study Drug

Study drug and placebo will be distributed by Sobi, the manufacturer of study drug, to the research pharmacy at each Clinical Center. Each Clinical Center research pharmacy will be responsible for maintaining detailed records regarding the receipt of study drug. General study drug accountability, participant-specific study drug accountability and, if necessary, Shipment Tracking Accountability logs will be maintained by the Clinical Center pharmacists. Documentation includes study drug receipt, storage, dispensing, and final disposition.

5.2.2 Return or Destruction of Study Drug

At the completion of the study, there will be a final reconciliation of study agent shipped, study agent consumed, and study agent remaining. This reconciliation will be logged on the study agent reconciliation form, signed and dated. Any discrepancies noted will be investigated, resolved, and documented before the return or destruction of unused study agent. Study agent destroyed on site will be documented in the study files.

5.3 Concomitant Therapy

Information about medication use will be collected at baseline and throughout the course of the study. Appropriate sources for obtaining this information include the participant, the medical/dialysis unit record, and treating clinicians.

6 Study Procedures

6.1 Study Visits and Activities

A schedule of study visits and procedures is provided in the Study Procedures Table in **Section 15.1**.

All blood collections will be performed either on a non-dialysis day, or before the initiation of dialysis on a dialysis day. Post-randomization study visits can take place in the dialysis unit or via phone.

6.1.1 Pre-screening Activities

Patients at participating dialysis units will be screened for eligibility. Clinical Center study personnel will review dialysis unit records and other medical records to assess eligibility. The treating nephrologist for a potentially eligible patient will be contacted to further assess eligibility and obtain permission to contact the patient.

6.1.2 First Screening Visit (Day –30 to Day –14)

Patients who appear eligible based on pre-screening will be approached in person to determine interest in participation and confirm eligibility. Study personnel will discuss the study goals and procedures with the potential participant in detail. If the patient agrees to participate in the study, study personnel will review and assess understanding of the entire informed consent form before obtaining written informed consent from the participant. The consenting process will be performed by a qualified investigator or study site designee. Informed consent will be obtained and documented before any study procedures are performed.

The screening activities may take place over a single visit or multiple visits.

Screening Activities

- Obtain informed consent
- Collect baseline data including demographics, medical history, and medication use
- Obtain blood for hsCRP (local Clinical Center laboratory and central laboratory), and CBC with differential (local laboratory). The hsCRP result from the local laboratory will be used for eligibility determination and a batched measurement made by the central laboratory on a stored sample will be used for determining the pre-treatment hsCRP value used in efficacy assessments. The blood obtained for the central laboratory measurement will be processed, aliquoted and stored at -80 °C for future batched shipping. If blood is obtained on a dialysis day, blood should be drawn before dialysis.
- Testing for tuberculosis, hepatitis B, hepatitis C, and HIV if clinical results are not available (at research team's discretion, can occur at Screening Visit 1 or 2).
- Review eligibility criteria

6.1.3 Second Screening Visit (Day –10 to Day –1)

The second screening visit should be performed within 10 days prior to the baseline/randomization visit and far enough in advance of the baseline/randomization visit to be sure that the results of the hsCRP (performed at the local laboratory), CBC with differential, and, if applicable, serum pregnancy test, will be available prior to baseline.

- Obtain blood for hsCRP (local Clinical Center laboratory and central laboratory), and CBC with differential (local laboratory). The hsCRP result from the local laboratory will be used for eligibility determination and a batched measurement made by the central laboratory on a stored sample will be used for determining the pre-treatment hsCRP value used in efficacy assessments. The blood obtained for the central laboratory measurement will be processed, aliquoted and stored at -80 °C for future batched shipping. If blood is obtained on a dialysis day, blood should be drawn before dialysis.
- Testing for tuberculosis, hepatitis B, hepatitis C, and HIV if clinical results are not available (at research team's discretion, can occur at Screening Visit 1 or 2).
- Obtain blood for serum pregnancy test for women of childbearing potential (local laboratory)
- Review eligibility criteria

6.1.4 Baseline/Randomization Visit (Day 0)

At the baseline visit medication use, vital signs, physical examination and adverse events will be recorded, and eligibility will be confirmed. After eligibility has been confirmed, a call will be scheduled for the participant to complete five telephone questionnaires (see section 6.1.13). Hand grip strength will be measured using a dynamometer.

Blood will be collected for serum, plasma, and buffy coat isolation for future DNA extraction. Samples will be aliquoted and stored at -80 °C for future batched shipping. Blood collection will be performed prior to dialysis initiation if performed on a dialysis day. If blood is not collected on the day of the Baseline/Randomization visit (Day 0), it will be collected pre-dialysis at the next dialysis session and prior to initiation of the study drug. The batched samples will include blood for hsCRP.

Randomization to treatment group will be performed through the centralized Data Management System.

6.1.5 Initiation of Study Drug Administration

Study drug administration will begin at a dialysis session within 1 week after the Baseline/Randomization Visit and continue through Week 24 at a frequency of 3 times per week. The study drug administration log will be completed after each administration to document the administration and any symptoms or adverse events that occur during the dialysis session.

6.1.6 Weeks 1, 2, and 3

Week 1 begins on the day of the first drug administration. During Weeks 1, 2, and 3 there will be an in-person or telephone contact to perform the following:

- Review clinical events

6.1.7 Weeks 4, 8, 16, and 20

The following will be performed at in-person visits which may take place at the dialysis unit:

- Blood collection for CBC with differential that will be performed at the local Clinical Center laboratory
- Blood collection for hsCRP that will be performed at the central laboratory
- Obtain blood for serum pregnancy test for women of childbearing potential (local laboratory)
- Recording of concomitant medications, and adverse events

6.1.8 Weeks 12 and 24 (End of Treatment Visit)

The following will be performed at in-person visits which may take place at the dialysis unit:

- Blood collection for serum and plasma. Samples will be aliquoted and stored at -80 °C for future batched shipping. The batched samples will include blood for hsCRP.
- Blood collection for CBC with differential that will be performed at the local Clinical Center laboratory

- Obtain blood for serum pregnancy test for women of childbearing potential (local laboratory)
- Recording of dialysis unit laboratory studies, concomitant medications, and adverse events
- Hand grip strength measurement using a dynamometer

6.1.9 Early Withdrawal Visit

If a participant withdraws from the trial before the Week 24 end of treatment visit an Early Withdrawal visit will be scheduled to conduct the assessments that otherwise would be performed at Week 24.

Participants who stop taking study drug are not considered early withdrawals and will be asked to continue to provide follow-up data on the study schedule and to participate in the assessment at Week 24.

6.1.10 Post-Treatment Period: Weeks 28 through 48

After the study drug treatment period, participants will be followed for an additional 24 weeks to collect additional information about safety. Visits will occur every 4 weeks. Participants who stop taking study drug before Week 24 will be followed for an additional 24 weeks following study drug discontinuation. Participants will be instructed that enrolling in another interventional study during this post-treatment period is not permitted.

Week 28

The following will be performed at in-person visits which may take place at the dialysis unit:

- Blood collection for serum and plasma. Samples will be aliquoted and stored at -80 °C for future batched shipping. The batched samples will include blood for hsCRP.
- Blood collection for CBC with differential that will be performed at the local Clinical Center laboratory
- Obtain blood for serum pregnancy test for women of childbearing potential (local laboratory)
- Recording of concomitant medications and adverse events
- Hand grip strength measurement using a dynamometer

Weeks 32, 36, 40, 44, and 48

Adverse events will be recorded.

6.1.11 Patient Reported Outcomes (PROs) Questionnaire Administration

The University of New Mexico Health Sciences Center Computer Assisted Telephone Interviewing (CATI) team will contact study participants at Baseline and Weeks 12, 24, and 28 to administer the following questionnaires via telephone:

- Beck Depression Index (BDI) II
- FACIT Fatigue Scale
- Illness Effects Questionnaire
- Dialysis Symptom Index
- KDQOL™ SF-12

The questionnaires will be administered on non-dialysis days. It is expected that completion of the questionnaires will take approximately 45 minutes. If participants are unable to complete the full battery of questionnaires at one time, they will be permitted to continue the interview on a subsequent day.

6.1.12 Pharmacokinetic and Pharmacodynamic Studies

Pharmacokinetic and pharmacodynamic studies will be performed on 12 participants. Blood will be collected for measurement of anakinra concentration and hsCRP assay according to the following schedule starting on the first day of study drug administration:

1. Sampling Day 1 (the first day of study drug administration and prior to a 48-hour interval between dialysis sessions): prior to dialysis initiation and at the end of the dialysis session
2. Sampling Day 2 (the non-dialysis day following the first day of study drug administration): at the same time as the Sampling Day 1 end-of-dialysis collection
3. Sampling Day 3 (the dialysis session approximately 48 hours after the Sampling Day 1 pre-dialysis blood draw): prior to dialysis initiation and at the end of the dialysis session
4. Sampling Day 4 (dialysis day, 4 weeks after the first day of study drug administration, and prior to a 48-hour interval between dialysis sessions): prior to dialysis initiation and at the end of the dialysis session
5. Sampling Day 5 (the non-dialysis day immediately following Sampling Day 4): at the same time as the Sampling Day 4 end-of-dialysis collection
6. Sampling Day 6 (the dialysis session approximately 48 hours after the Sampling Day 4 pre-dialysis blood draw): prior to dialysis initiation and at the end of the dialysis session

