1.4.3 Dosing of Anakinra in Renal Impairment

Renal excretion accounts for a substantial proportion of the elimination of anakinra. The half-life with subcutaneous administration is 4-6 hours in patients with rheumatoid arthritis. As reported in the FDA product label, in mild renal impairment (creatinine clearance 50-80 ml/min) and moderate renal impairment (creatinine clearance 30-49 ml/min), the mean plasma clearance was reduced by 16% and 50%, respectively. For patients with severe renal impairment (creatinine clearance less than 30 ml/min) and end-stage renal disease, the mean plasma clearance was decreased by 70% and 75%, respectively. The recommended dose of anakinra for patients receiving maintenance hemodialysis is 100 mg subcutaneous every other day (from FDA product label).

The pharmacokinetics of anakinra with intravenous administration have been studied in individuals with normal kidney function and various degrees of renal impairment²⁶. Among individuals receiving maintenance hemodialysis, the mean plasma clearance of anakinra was 18.2 ± 3.2 ml/min compared with 137 ± 21 ml/min in individuals with normal kidney function. The mean half-life of anakinra administered intravenously at a dose of 1 mg/kg was 7.15 hours in hemodialysis patients compared with 2.64 hours in those with normal kidney function. The plasma concentrations of anakinra at 24, 48, and 72 hours after drug administration were similar with intravenous and subcutaneous administration.

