1.4.4 Dose Rationale for ACTION Trial

The recommended dose of anakinra for patients with rheumatoid arthritis is 100 mg per day administered subcutaneously. The recommended dose of anakinra for Cryopyrin-Associated Periodic Syndromes (CAPS) is 1 - 2 mg/kg daily with a maximum dose of 8 mg/kg. For patients with severe renal impairment (creatinine clearance less than 30 ml/min) or ESRD, it is recommended that the prescribed dose be administered every other day. In the previous published trial of anakinra in hemodialysis patients, the dosing schedule was 100 mg three times per week. This is the schedule that will be used in the ACTION trial²⁵. With dialysis schedules of Monday, Wednesday, and Friday or Tuesday, Thursday,

and Saturday, participants will receive anakinra every other day for 2 of the 3 doses each week, and every 3rd day for one of the 3 doses each week. As described in Section 1.4.3, pharmacokinetic studies suggest that for patients receiving hemodialysis, the same dosing schedule can be used for intravenous and subcutaneous administration of anakinra²⁶.

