7.4.3 Interim Analysis

The pharmacokinetic and pharmacodynamic data will be analyzed after 12 participants have completed the assessments in order to allow modification of dosing if indicated based on anakinra concentrations or CRP concentrations.

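### The PK/PD schedule in 6.1.12 does not by design sample the weekly 3-day dosing interval, although 7.4.3 lets these data modify dosing; an end-of-gap value arises only by accident of start day

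*Combined protocol and SAP*

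**What the plan says.** Section 1.4.4 cites a recommendation for severe renal impairment or ESRD: "it is recommended that the prescribed dose be administered every other day". Section 1.4.3 cites the same frequency for hemodialysis from the product label. Section 1.4.4 then describes the trial's own pattern on Monday/Wednesday/Friday or Tuesday/Thursday/Saturday dialysis: "every other day for 2 of the 3 doses each week, and every 3rd day for one of the 3 doses each week".

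Section 6.1.12 sets two sampling blocks in 12 participants, each measuring anakinra concentration and hsCRP. Sampling Day 1 is "the first day of study drug administration and prior to a 48-hour interval between dialysis sessions". Sampling Day 4 is a "dialysis day, 4 weeks after the first day of study drug administration, and prior to a 48-hour interval between dialysis sessions". Each block has a draw about 24 h after the end of dialysis and closes at the next session; for the second block this is "the dialysis session approximately 48 hours after the Sampling Day 4 pre-dialysis blood draw". Days 1, 3, 4 and 6 each have a pre-dialysis and an end-of-dialysis draw.

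Section 7.4.3 gives the purpose: the data are analyzed once 12 participants have completed the assessments, "in order to allow modification of dosing if indicated based on anakinra concentrations or CRP concentrations". It does not say which samples enter that analysis or how troughs are grouped.

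Section 5.2 places the dose in the last 30 minutes of the dialysis session, so a pre-dialysis draw is the trough of the interval just ended.

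**The concern.** The 3-day interval is the only part of the week in which the trial spaces doses more widely than the recommendation it cites. If any interval calls for deliberate sampling before a decision on dosing, it is this one. The sampling rule instead selects sessions followed by the shorter interval, and the documents give no reason for that.

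Two things are at stake. First, the interim look may have few or no values of drug concentration and hsCRP at the end of the long interval, and the plan does not control how many. Second, the rule fixes the interval after Sampling Day 4 but not the interval before it. The Day 4 pre-dialysis trough can therefore belong to either a 48-hour or a 72-hour interval. A summary that pools these values, or compares them with the first-dose trough, would be affected by the weekday on which each participant started.

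**Working it through.** **Inputs.** Dosing days: 1.4.4. Sampling rule: 6.1.12. Dose at the end of the session: 5.2. Intravenous half-life: 1.4.3 ("The mean half-life of anakinra administered intravenously at a dose of 1 mg/kg was 7.15 hours in hemodialysis patients"). Assumptions not in the documents: a session of about 4 h, one-compartment decay, and no carry-over from earlier doses.

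**Step 1: the plan's own pattern.** Monday/Wednesday/Friday gives intervals of 48, 48 and 72 h, which sum to 168 h. Tuesday/Thursday/Saturday gives the same. This reproduces the description in 1.4.4.

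**Step 2: which start days 6.1.12 allows.** Four weeks is 28 days, so Sampling Day 4 falls on the same weekday as Sampling Day 1.

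| Start session | Interval after it | Allowed | Interval before the Day 4 pre-dialysis draw | Interval before the Day 6 pre-dialysis draw |
|---|---|---|---|---|
| First (Mon or Tue) | 48 h | yes | 72 h | 48 h |
| Second (Wed or Thu) | 48 h | yes | 48 h | 48 h |
| Third (Fri or Sat) | 72 h | no | 48 h | 72 h |

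The only start that would carry a block through the long interval is excluded. Of the two allowed starts, one yields a single end-of-gap sample out of 2+1+2+2+1+2 = 10 draws, and the other yields none. Across the 12 participants the count can be anything from 0 to 12.

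**Step 3: time since dose.** The intervals run from one pre-dialysis time to the next, and the dose comes at the end of the session. The trough is thus at about 48 − 4 = 44 h or 72 − 4 = 68 h.

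**Step 4: expected concentration.** Fraction remaining = 2^(−t/7.15).
- At 44 h: 2^(−6.15) = 0.0140, or 1.4%.
- At 68 h: 2^(−9.51) = 0.00137, or 0.14%.
- Ratio: 2^(24/7.15) = 10.2.

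With an assumed half-life from 5 to 20 h, the ratio runs from about 28 down to 2.3. The direction does not change.

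**Step 5: effect of pooling.** Suppose, for illustration, that half of the treated participants are first-session starters. The mean Day 4 trough is (1.4 + 0.14)/2 = 0.77% of the end-of-dialysis concentration. That is 1 − 0.77/1.4 = 45% below the first-dose trough on Sampling Day 3, and the whole difference comes from start day. Day 3 against Day 6 is a matched comparison for everyone, at about 44 h each.

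**Step 6: how much of the week is affected.** The first 48 h of the long interval follow the same post-dose course that is sampled elsewhere. The additional part is 72 − 48 = 24 h, and 24/168 = 14% of the week.

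**The case against.** A reader might infer that the long gap is never observed. The documents do not support that: a first-session starter does have an anakinra and hsCRP value at its end. A reader might also count the whole 72 h, or 72/168 = 43% of the week, as unobserved. Only the last 24 h goes beyond what the 48-hour blocks cover.

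The other side has further arguments. At the cited half-life, little drug remains even at 44 h, so near-complete elimination will already be visible in the sampled interval, and the 10-fold ratio compares two small values. The 24 h and 44 h samples allow some extrapolation of concentration. Section 1.4.3 cites external concentrations out to 72 h. Section 1.4.4 notes that the earlier hemodialysis trial used the same three-times-weekly schedule, and 1.3.1 reports a 53% fall in mean hsCRP on active treatment there. Main-trial hsCRP draws have no fixed weekday (6.1), so some may follow the long gap. Finally, 7.4.3 speaks of modifying dosing in general and does not mention the interval.

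Most of this stands for concentration, and it lowers the severity. It does not settle CRP, which 7.4.3 names as a basis for modification. The cited 72 h data compare routes of administration by concentration. The pilot's average reduction does not describe the course of CRP within a week. The main-trial draws are outside the 6.1.12 schedule, and nothing requires them to fall after the long gap. The mixing of Day 4 troughs is untouched by any of these arguments.

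**Conclusion.** The point holds as a gap in design and specification, of minor to moderate severity. The PK/PD schedule does not by design sample the 3-day interval. What it captures there is one end-point value per first-session starter, in an uncontrolled number of participants, and 7.4.3 does not separate those values from 48-hour troughs. The expected difference between the two kinds of trough is about 10-fold at the cited half-life, and 2.3- to 28-fold over the assumed range of 5 to 20 h. These figures rest on one-compartment decay; the 1.4% and 0.14% levels also rest on a 4 h session. The documents give no basis for calculating how far CRP rebounds in the last 24 h of the gap.

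Section 6.1.12 does not limit the 12 participants to the active arm. If they follow the 1:1 allocation in 7.2 (an assumption), about 6 receive anakinra, and the informative end-of-gap values are fewer still.

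It would go too far to conclude that the substudy cannot inform dosing, or that the dosing schedule is wrong. The first is not supported because 24 h and 44 h data are collected in every participant; the second is not a matter that these passages decide. What is needed is that 1.4.4, 6.1.12 and 7.4.3 be reconciled before the interim look.

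**What to change.** This concerns sampling and analysis only; no dose or dosing schedule is proposed.

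1. In 6.1.12, require Sampling Day 4, and so Sampling Day 1 four weeks earlier, to be the first dialysis session of the week. This is one of the start days already allowed, and it still precedes a 48-hour interval. The Day 4 pre-dialysis draw then ends the 3-day gap and the Day 6 pre-dialysis draw gives the 48-hour trough in the same participant, in all 12. The Day 3 and Day 6 troughs remain comparable.
2. In 7.4.3, state that anakinra and hsCRP troughs are analyzed by length of the preceding interval and that Day 4 and Day 6 troughs are not pooled.

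Cost: the draws stay at 10 and no visit is added. Substudy participants can start on only one weekday per dialysis schedule; the window of 1 week after the baseline visit in 6.1.5 has room for this. The long gap would still be seen at its end point and not as a full profile.

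Moving the Week 4 block to the last session of the week would give a fuller profile. However, it would put every Sampling Day 5 draw on a Saturday or Sunday and would require the interval wording in 6.1.12 to be rewritten. The first-session option gains most of the information at lower cost.
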